2.1.1. Overall Survival

2.1.2 Change in HIV viremia at first transfusion, as measured by RNA PCR, from pre-transfusion level to the level one-week post transfusion.

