2.2. Secondary Objectives

In Patients with HIV requiring RBC transfusion, to compare leukocyte reduced RBC versus non-leukoreduced RBC transfusions with respect to:

2.2.1. Time to death or first new serious HIV-related complication.

Endpoints include selected new AIDS defining conditions and serious bacterial infections. The criteria for selection were that the condition has a median survival of less than one year or an acute mortality of >5%. Additionally, in most cases only definitively diagnosed conditions were selected.

These diseases include: disseminated fungal infections (cryptococcus, coccidiomycosis, histoplasmosis), invasive cervical carcinoma, cryptosporidium, CMV disease, visceral Kaposi's sarcoma, lymphoma, progressive multifocal leukoencephalopathy (PML), disseminated *Mycobacterium avium* complex or atypical mycobacterium, tuberculosis, *Pneumocystis carinii* pneumonia, toxoplasmosis and bacterial infections of a normally sterile site (bloodstream, CSF, etc.). See Section 7.5 for details.

2.2.2. Time to new CMV end organ disease, in patients with no prior CMV disease. Incidence of new CMV end organ disease or progression of existing CMV disease, in patients with prior CMV disease.

2.2.3. Among patients with detectable CMV viremia, change in quantitative CMV from pre-transfusion level to one-week post transfusion level. Among patients with non-detectable CMV viremia, percent positive after transfusion, and CMV level in those who do become positive.

2.2.4. Slope of HIV & CMV viral load over time, excluding 28-day periods after initiation of each transfusion episode. This endpoint will measure the long-term effect on viral load, excluding the immediate post-transfusion periods.

2.2.5. Incidence of individual HIV-related complications and infections described in Section 7.5.

2.2.6. Change in cytokine and lymphocyte activation marker levels from baseline to one week: TNF, TNF receptor, IL-6, β_2 M.

2.2.7. Change in lymphocyte markers, including CD4, CD8 and activated subsets (CD8+CD38+, CD8+HLA-Dr+).

2.2.8. Functional status (Karnofsky) and quality of life.

2.2.9. Persistence of donor lymphocytes in the recipient at one and three months after initial transfusion.

2.2.10. Area under the curve (AUC) of HIV and CMV viral load over 3-months post transfusion.

2.2.11. Other measures of change in viral load, such as change from baseline to mean level over weeks

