- 8.4.1 Laboratory Specimens: At weeks 1 (\pm 1 day), 2, 3, 4 (\pm 2 days) and every 3 (\pm 1 month) months after the first enrollment transfusion episode begins, blood specimens will be obtained, processed and frozen for batch shipment to the central laboratory. In addition, central lab blood specimens will be obtained within 72 hours pre-transfusion and at weeks 1 (\pm 1 day), 2, 3 and 4 (\pm 2 days) following the beginning of the second transfusion episode (see section 7.1). If the pre-transfusion blood draw is missed at the second transfusion episode, the weekly blood draws should be skipped and obtained instead at the third transfusion episode. If the second transfusion episode begins during the first 28 days of the initial episode, cancel any remaining weekly blood draws associated with the first episode and start over for the second episode. If there is a quarterly clinical visit during the 28-day period following the second transfusion episode, both the weekly blood draws and the quarterly blood draws should be obtained, if possible. The weekly blood draw and local (CBC with differential and platelets) samples should take precedence over the quarterly central labs if both cannot be obtained. Blood specimens will also be obtained for local testing at entry and at each quarterly visit. These have lower priority than specimens for the Central Lab.
- 8.4.1.1 Obtain 7 ml EDTA (purple) tube , 7 ml ACD (yellow) tube, and 7 ml red top tube for each scheduled central laboratory blood draw. These specimens will be sent to the clinical site lab which will aliquot them and ship to central lab as per Laboratory Procedures section of the VATS Study Manual.
 - 8.4.1.2 Parameters measured at Central Lab:

1. EDTA blood: CD4 and CD8 counts (and activated lymphocyte subsets), donor WBC survival, IL-6, TNF, and storage.
 2. ACD blood: Quantitative CMV testing, HIV plasma RNA PCR, and storage.
 3. Serum: TNF-R EIA, β_2 -microglobulin EIA, EPO RIA, CMV EIA screen, HIV-1 EIA screen, and storage.
- 8.4.1.3 Obtain EDTA (purple top) tube for local CBC with differential and platelet count testing every 3 months during the study.

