So, for example, if a log rank test has p-value $<.008$ at 22 months the stopping rule would dictate termination of the trial with an overall false-positive rate of 5%. Of course in practice, crossing a sequential boundary should trigger further review of other endpoints, and should not be considered as a hard and fast rule for early stopping. Assuming medians of 12 and 16 months in the two treatment groups, a total of 427 events would be expected after 34 months. The "information time" is the fraction of these 427 events expected at each interim analysis. This results in 83% power for detecting a four month difference in median survival of 12 versus 16 months. The calculations are based on a constant failure rate assumption, although the actual analysis will be with a log rank test. The calculations are relevant for the power of a log rank test, if the hazard ratio is the same as the ratio of medians assumed above, i.e., $1.33 = 16 \div 12$. In the actual trial, the exact numbers of events in the "number deaths" column will not be observed at the specified time points. The Lan and DeMets procedure can then be used to determine the appropriate nominal p-values at the times of the interim analyses, depending on the actual numbers of events observed.

The basic analysis of viral activation will involve calculating, within each patient, the ratio of HIV viral load (as measured by RNA PCR copy number) measured one week after initial transfusion, divided by the pre-transfusion copy number. It will be assumed in the following that the logarithm of this ratio is normally distributed, and a two-sample T-test will be used for comparing groups with respect to log ratio. Thus, the endpoint for each patient is the change in viral load on a logarithmic (base 10) scale. Even if the normal distribution is not a good approximation in this case, the T-test is known to be quite robust to violations of this assumption with the sample sizes being considered.

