In pilot data from 10 cases given non-leukoreduced transfusions, the mean change in viral load from pre-transfusion to 7 days post-transfusion was .15 logs (base 10) with a standard deviation of .484 logs, i.e., about a half a power of 10. Six hundred forty cases will provide 97% power for detecting a .15 log difference between the treatments with respect to mean log change in viral load. Even if 50% of cases are missing sufficient data to evaluate this endpoint, (320 cases with data) the power would still be 79%. A treatment difference of .15 logs is a 1.41-fold difference. However, it is felt that a much larger difference, on the order of at least 5-fold difference (.7 logs), would likely be required to have a clinically meaningful effect. Even with a standard deviation of 1.0 logs there is $>93\%$ power for detecting a .7 log treatment difference with a much smaller sample size of 100 patients (50 per group).

Note that the primary clinical endpoint is driving the sample size requirements for the trial rather than the primary laboratory endpoint. This reflects the absence of knowledge about whether a biological effect on viral load would

have any clinical implication for the patient. Thus, the early stopping rule is specifically designed to be based on the clinical endpoint. Even if an early, convincing treatment difference in viral activation is observed, this should not be sufficient for early termination of the trial.

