11.3 Analysis Plans

The primary analysis for the time-to-event endpoint will be the logrank test. The primary analysis for the change in viral load will be the t-test. In other analyses proportional hazards models will be used to adjust treatment comparisons for covariates and to explore the effects of covariates themselves. Short-term changes in viral load will be based on log change from baseline, using two-sample t-tests or a Wilcoxon test if Normal assumptions are violated even after transformations. Covariates will be incorporated using Analysis of Variance. Random effects models will be used to analyze slopes of cytokines, lymphocyte markers and viral load over time. Incidence of individual events will be summarized by calculating number of events per Person-year and compared with Poisson methods. For example, the number of new diagnoses of CMV end organ disease, or diagnoses of CMV progression, will be counted and divided by the number of person-years of followup in order to estimate an incidence rate for CMV events, and compared with Poisson methods. (Note that a single person can have more than one CMV event.) In addition, person-specific incidence rates for each of several event types will be compared with two-sample Wilcoxon tests. The test statistics can be combined into an overall test using methods of Wei and Johnson⁶⁶.

Section 12 -- References

1. Centers for Disease Control: 1993 revised classification system for HIV infection and expanded surveillance case definition for AIDS among adolescents and adults. *MMWR* 1992;41(RR-17):1-19.

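### The primary viral-load t-test uses only patients with both a pre-transfusion and a week-1 sample; a repeated-measures estimate of the same week-1 difference would use the week 2 to 4 samples too, for a modest gain

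*Protocol*

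**What the plan says.** Section 2.1.2 makes this a primary objective: "Change in HIV viremia at first transfusion, as measured by RNA PCR, from pre-transfusion level to the level one-week post transfusion". Section 11.2 defines each patient's value as the HIV RNA copy number "measured one week after initial transfusion, divided by the pre-transfusion copy number", on a log10 scale, and says "a two-sample T-test will be used for comparing groups with respect to log ratio". Section 11.3 confirms it: "The primary analysis for the change in viral load will be the t-test".

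On power, Section 11.2 states: "Six hundred forty cases will provide 97% power for detecting a .15 log difference between the treatments". It then gives the missing-data case: "Even if 50% of cases are missing sufficient data to evaluate this endpoint, (320 cases with data) the power would still be 79" percent. It does not discuss whether the patients with data might differ from those without.

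Under Section 8.4.1, at weeks 1 (±1 day), 2, 3 and 4 (±2 days) after the first episode begins, "blood specimens will be obtained, processed and frozen for batch shipment to the central laboratory"; HIV plasma RNA PCR is among the central tests. If a second episode starts within the first 28 days, the first episode's remaining weekly draws are cancelled.

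The later weeks serve secondary measures: area under the curve over three months (2.2.10) and, in 2.2.11, others "such as change from baseline to mean level over weeks" 1 to 4, together with change to individual time points. Section 11.3 plans random effects models for viral-load slopes, not for the week-1 comparison.

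**The concern.** A within-patient ratio exists only when both samples exist. The named primary test is therefore a complete-case analysis, and the power text treats it as one by turning 50% missing into 320 analysed patients.

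This has two consequences. First, precision goes unused: a patient who misses the day-7 draw but attends at weeks 2 to 4 has given samples that help predict the missing value. Week 1 also has the narrowest collection window, in patients who may enter with a Karnofsky score as low as 40 and whose assumed control median survival is 12 months. Second, the t-test on complete cases takes the absence of a sample to be unrelated to the change in virus level within each arm. A likelihood model that includes the later values needs less: absence may depend on virus levels that were observed.

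The issue is missing values. It is separate from whether the comparison should be adjusted for the baseline level.

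**Working it through.** **Inputs from the protocol (Section 11.2):** difference .15 log10; SD .484 (10 pilot cases, all non-leukoreduced); 320 per arm; stress case 160 per arm. Two-sided α = .05 is stated for survival and assumed here for viral load.

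**Inputs not in the protocol, so assumed:**
- ρ, the common correlation among the changes from baseline at weeks 1 to 4: .3, .5, .7, with .9 as an extreme.
- q, the share of patients missing week 1 who have a baseline and all of weeks 2 to 4: 0, .5, 1.

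ρ = .5 is a natural reference. If log10 values have equal variance and the same correlation r between any two visits, two changes sharing one baseline have covariance proportional to 1 − r and variance proportional to 2(1 − r). Their correlation is ½ whatever r is.

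**Step 1: reproduce the plan.** Power ≈ Φ(δ / (σ√(2/n)) − 1.96), n per arm.
- n = 320: .15 / (.484 × .0791) = 3.92; Φ(1.96) = 97.5% (stated 97%).
- n = 160: .15 / (.484 × .1118) = 2.77; Φ(.81) = 79.2% (noncentral t: 78.9%; stated 79%).
- n = 50, δ = .7, SD 1.0: .7 / .2 = 3.5; Φ(1.54) = 93.8% (stated as above 93%).

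All three agree; there is no arithmetic error.

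**Step 2: t-test power at other missing rates.** 10% missing: 96.1%; 20%: 93.9%; 30%: 90.7%; 50%: 79.2%.

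**Step 3: add weeks 2 to 4 under missing-at-random.** Let m be the share missing week 1. The squared multiple correlation of the week-1 change with three later changes is R² = 3ρ² / (1 + 2ρ). Relative to full data, the variance of the week-1 difference is multiplied by

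f = (1 − R²)/(1 − m) + R²/(1 − m + mq),

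and the effective total sample is 640/f. Example with m = .5, ρ = .5, q = .5: R² = .75/2 = .375; f = .625/.5 + .375/.75 = 1.75; 640/1.75 = 366.

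| ρ | R² | Effective N, q = .5 to 1 | Share of the 320 lost that is recovered | Power |
|---|---|---|---|---|
| .3 | .169 | 339 to 349 | 6% to 9% | 81.4% to 82.6% |
| .5 | .375 | 366 to 394 | 14% to 23% | 84.2% to 86.8% |
| .7 | .612 | 402 to 461 | 26% to 44% | 87.4% to 91.4% |
| .9 | .868 | 450 to 565 | 41% to 77% | 90.8% to 95.8% |

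At q = 0 power stays at 79.2%. Simulation (4,000 trials per setting) gave 83.2% and 86.4% at ρ = .5, and 87.0% and 91.2% at ρ = .7, for q = .5 and 1, against about 79% for the t-test.

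**Step 4: limits of the calculation.** It treats the whole 50% as missing week 1, whereas the protocol's phrase also covers a missing pre-transfusion sample. It assumes all three later samples in each recoverable patient, so cancelled draws lower the gain. It counts no gain from baseline adjustment.

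**Step 5: the larger effect.** At .7 log and SD 1.0 with 160 per arm, .7 / .1118 = 6.26, and 6.26 − 1.96 = 4.30, so power exceeds 99.9% without the later samples.

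**The case against.** The strongest reply is that the plan is coherent: its figures reproduce, its test is named, and a more efficient method is a preference. Missing-data handling may also sit in an analysis plan not shown. Part of this stands, since nothing is miscalculated. But the protocol itself fixes the primary test and what enters it, so the choice is open to comment here.

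A reader might infer that the plan permits losing half its patients. It does not: the 50% is an even-if case showing how far power holds up, not an expected or tolerated rate.

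A reader might also infer that weeks 2 to 4 would recover most of the loss. The documents give neither ρ nor q, and recovery passes half only at ρ of about .8 or more with nearly all later samples present. Some later draws are cancelled by rule. Section 6.1 discourages new antiretrovirals only for two weeks after an episode, so weeks 3 and 4 may reflect changed therapy and predict week 1 less well.

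A third inference, that the t-test result is biased, is not shown either. With a 12-month median and constant hazard, death by day 7 is about 1 − .5^(7/365) = 1.3%. Patients and care staff are blinded, and missingness acting alike in both arms does not by itself create a false difference. Patients too ill for every weekly draw are not recovered by either method.

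Finally, the t-test needs no model across weeks, so the covariance structure is an added assumption. That stands as a real cost.

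Two replies to the proposal fail. The secondary measures at weeks 1 to 4 do not recover the week-1 contrast; averaging over weeks would change what is estimated. And a missing pre-transfusion sample does not exclude a patient from the proposed model, because a common baseline mean lets the week-1 value contribute.

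**Conclusion.** The point holds in a limited form. The primary viral-load test discards patients without both samples, the plan treats that only as lost power, and samples already scheduled in the same episode could inform the same contrast.

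In the 50% stress case the power gain is about 2 to 3 points at ρ = .3, 5 to 8 at ρ = .5 and 8 to 12 at ρ = .7, for q from .5 to 1. These rest on assumed ρ and q, on missing-at-random, and on an SD from 10 pilot cases. The gain shrinks with cancelled draws. It is of little consequence when few values are missing, or near the .7 log difference that Section 11.2 regards as likely needed for clinical meaning.

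The change in assumption, from complete cases being representative within arm to missing-at-random given observed virus levels, is a further reason to act. The documents do not show how much bias, if any, it would avoid. This is a worthwhile low-cost improvement, not an error that invalidates the comparison.

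**What to change.** In Section 11.3, make the primary viral-load result the week-1 arm difference from one likelihood-based repeated-measures model of log10 HIV RNA at baseline and weeks 1, 2, 3 and 4 of the first episode. Specify week-by-arm effects, an unstructured covariance and a baseline mean common to both arms. Include every randomized patient with at least one of these samples. Keep the two-sample t-test on patients with both samples as a supportive analysis. Amend Section 11.2 to match, leaving the 79% as the power of the complete-case test.

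The endpoint, visits, samples and sample size do not change. The cost is wording and programming. The downside to state openly is reliance on missing-at-random and on a covariance model that the t-test does not need.

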11.3 Analysis Plans

The primary analysis for the time-to-event endpoint will be the logrank test. The primary analysis for the change in viral load will be the t-test. In other analyses proportional hazards models will be used to adjust treatment comparisons for covariates and to explore the effects of covariates themselves. Short-term changes in viral load will be based on log change from baseline, using two-sample t-tests or a Wilcoxon test if Normal assumptions are violated even after transformations. Covariates will be incorporated using Analysis of Variance. Random effects models will be used to analyze slopes of cytokines, lymphocyte markers and viral load over time. Incidence of individual events will be summarized by calculating number of events per Person-year and compared with Poisson methods. For example, the number of new diagnoses of CMV end organ disease, or diagnoses of CMV progression, will be counted and divided by the number of person-years of followup in order to estimate an incidence rate for CMV events, and compared with Poisson methods. (Note that a single person can have more than one CMV event.) In addition, person-specific incidence rates for each of several event types will be compared with two-sample Wilcoxon tests. The test statistics can be combined into an overall test using methods of Wei and Johnson⁶⁶.

Section 12 -- References

1. Centers for Disease Control: 1993 revised classification system for HIV infection and expanded surveillance case definition for AIDS among adolescents and adults. *MMWR* 1992;41(RR-17):1-19.

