4.2. Stratification Factors

Randomization will be stratified by CD4 or total lymphocyte count and by CMV disease. A dynamic balancing method⁵⁷ will also be used to ensure treatment balance within each institution.

4.2.1. CD4 or Total Lymphocyte Count. For purposes of this stratification factor, CD4 count history should be based on medical record or physician report. If these are not available, CD4 count may be based on patient self-report if the clinical coordinator judges it to be reliable. The two levels of this stratification factor are:

4.2.1.1. CD4 count $<50/\mu\text{L}$ at any time in the past. In cases where CD4 count was never known to be $<50/\mu\text{L}$ and there is no history of $\text{CD4} \geq 50$ within the past month, total lymphocyte count $< 1000/\mu\text{L}$ within one week prior to study entry.

4.2.1.2. Not meeting criteria 4.2.1.1 (i.e., available documentation or reports suggest $\text{CD4} \geq 50/\mu\text{L}$, within the past month, or in absence of this information, total lymphocyte count $\geq 1000/\mu\text{L}$ within one week prior to study entry).

4.2.2. CMV Disease. (All patients must have evidence of current or past CMV infection.) The two levels of this stratification factor are:

4.2.2.1. Current or previous diagnosis of CMV end organ disease (excluding viremia alone; see sections 7.3 and 7.4).

4.2.2.2. No current or previous diagnosis of CMV end organ disease.

4.3. Patients are registered and randomized with the following procedure.

4.3.1. Verify eligibility criteria (see sections 3 and 8.1), ascertain stratification factors, (sections 4.2 and 8.1.3) and obtain signed informed consent. Clinic Randomization Form is completed. Eligible patients are assigned the next sequential patient ID number.

4.3.2. Call the coordinating center (NERI) at [contact] from a touch tone phone. The caller will be asked questions to ascertain clinical site, patient ID number, eligibility, and stratification factors. The caller will receive a coded treatment assignment in the form of a five digit number.

- 4.3.3. If phone is busy, wait five minutes and try again. If after three tries the phone is still busy, or if phone call does not go through, open the next sequential sealed envelope. The envelope will contain a coded treatment assignment in the form of a five digit number. Call the VATS Data Manager at [contact], [name] to report the problem. Go to step 4.3.4.

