11.1 Design

This trial will be a two-group, double-blind, randomized trial comparing standard non-leukoreduced red blood cell (RBC) transfusions with leukoreduced RBC transfusions in 640 patients. Randomization will be stratified by CD4 history (or total lymphocyte count; see below) and by CMV end organ disease. All patients must be CMV seropositive.

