11.2 Sample Size Considerations

The total accrual goal for this trial is 640 patients (320/arm) accrued over 22 months, with 12 months of additional follow-up. This sample size ensures 83% power for the primary endpoint of overall survival. Details of this calculation follow.

Preliminary data from three of the VATS sites and from ACTG trial 993 suggest a baseline median survival from first transfusion of less than one year. One site provided raw data on 45 cases at first transfusion. The estimated median survival was 7 months with 6, 12 and 18-month survival probabilities of 53%, 34% and 26%, respectively. Another site reported that after one year follow-up of 15 consecutive first-transfusion cases, 9 had died, for a one-year survival of 40%. A third site reported a median survival of 11 months and a 34-month survival of 20%. The 6, 12 and 18-month survival probabilities from first transfusion, among patients in ACTG 993 (a trial for patients with CD4 counts $< 50/\mu\text{L}$) were 73%, 53% and 39%, respectively⁵⁹. Although the data from the VATS sites suggest shorter durations of survival (medians of 7 to 11 months) than the ACTG trial (median > 12 months), it is projected that the ACTG results may reflect more accurately what to expect in the VATS, since patients who enter clinical trials often have a better prognosis than patients in consecutive series. A median survival of 12 months in the control group will be assumed. An improvement from 12 months in the non-leukoreduced to 16 months in the leukoreduced RBC group would be considered an important treatment difference.

Assuming an annual accrual rate of 350 per year, 640 patients can be accrued in 22 months. With a fixed sample size design, 640 patients provide 84% power for a two sided $\alpha = .05$ test, using sample size formulae of Schoenfeld and Richter^{61,65}.

However a group sequential procedure based on the methodology of Lan and DeMets⁶² using an O'Brien-Fleming boundary⁶³ will be used to monitor the trial for possible early stopping, with formal interim analyses at 22, 28 and 34 months from study activation. Repeated looks at the data result in a slight loss of power. This design has 83% power while controlling Type I error at 5% (two-sided), as detailed in the table.

Months	Nominal P-Value	Pr(Reject H_0 H_1)	Number Deaths	Info Time
22	.008	.36	258	.61
28	.026	.33	357	.84
34	.041	.14	427	1.00
		.83 (= power)		

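### Stratifying the primary log-rank test by the two randomization factors (CD4/lymphocyte count and CMV disease) is a nearly free efficiency gain; the stated 83% power is not an error

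*Protocol*

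**What the plan says.** Protocol 4.2 states: "Randomization will be stratified by CD4 or total lymphocyte count and by CMV disease". Section 11.1 repeats it: "Randomization will be stratified by CD4 history (or total lymphocyte count; see below) and by CMV end organ disease". Two levels of each factor give four strata. In addition, a dynamic balancing method "will also be used to ensure treatment balance within each institution".

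On analysis, Protocol 11.3 says: "The primary analysis for the time-to-event endpoint will be the logrank test". It does not say whether the test is stratified. Covariates come later: "In other analyses proportional hazards models will be used to adjust treatment comparisons for covariates".

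On power, Protocol 11.2 gives the fixed design first ("With a fixed sample size design, 640 patients provide 84% power for a two sided" 5% test) and then the sequential one: "This design has 83% power while controlling Type I error at 5% (two-sided), as detailed in the table". It uses one constant death rate per arm, with medians of 12 and 16 months and no strata. It also states a condition: "The calculations are relevant for the power of a log rank test", provided that the hazard ratio equals the ratio of medians, 1.33.

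**The concern.** Stratified randomization removes most of the chance imbalance between arms in the stratification factors. An ordinary log-rank test still counts that imbalance as a source of variation, so when the strata predict death its variance is somewhat too large and its true size falls below the nominal level. Pooling patients with different death rates also brings the overall hazard ratio closer to 1 than the ratio within each stratum. Both effects cost power.

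Overall survival sets the sample size and is the only endpoint with a stopping rule, so any efficiency lost here is lost on the trial's main question. The strata are recorded at randomization, so using them needs no new data.

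**Working it through.** **Step 1. Reproduce the stated power.** Inputs from Protocol 11.2: 320 patients per arm, uniform accrual over 22 months, analysis at 34 months, medians of 12 and 16 months.

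- With hazard λ = ln 2 / median, the probability of death by month 34 is 1 − [exp(−12λ) − exp(−34λ)] / (22λ).
- Control: 1 − (0.5000 − 0.1403)/1.2708 = 0.7170, giving 229.4 deaths. Leukoreduced: 1 − (0.5946 − 0.2293)/0.9531 = 0.6167, giving 197.3 deaths. The total is 426.8 (stated 427).
- Fixed power (Schoenfeld): √427/2 × ln(16/12) = 10.332 × 0.2877 = 2.972; Φ(2.972 − 1.960) = 84.4% (stated 84%).
- Sequential power, with nominal p-values .008, .026 and .041 at 258, 357 and 427 deaths: rejection probabilities .366, .329 and .140, total 83.5% (stated .36, .33, .14, total .83). Overall type I error is 4.97%.

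The protocol's figures hold for an ordinary log-rank test.

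**Step 2. Simulate stratified randomization with prognostic strata.** Permuted blocks within four strata, looks at 22, 28 and 34 months, the stated nominal p-values, 5,000 trials per case. The 62% with CD4 below 50 comes from the one-site data set in Protocol 11.1. Assumptions not in the documents: 20% with CMV disease, the stratum hazard ratios in the table, and a within-stratum treatment hazard ratio of 0.75. Control median is held at 12 months.

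| Stratum hazard ratio, CD4 / CMV | Power, unstratified | Power, stratified | Type I, unstratified | Type I, stratified |
|---|---|---|---|---|
| 1 / 1 | 84.0% | 83.6% | 4.8% | 4.9% |
| 1.25 / 1.25 | 83.5% | 83.9% | 4.7% | 4.7% |
| 1.5 / 1.25 | 81.4% | 82.2% | 4.5% | 4.7% |
| 1.5 / 1.5 | 81.6% | 83.3% | 4.9% | 5.3% |
| 2 / 1.5 | 79.4% | 82.2% | 4.4% | 4.9% |
| 2 / 2 | 77.9% | 82.7% | 3.7% | 4.8% |

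The simulation standard error is about √(0.82 × 0.18/5000) = 0.5 points for power and √(0.05 × 0.95/5000) = 0.3 points for type I error. Both tests were applied to the same simulated trials. Balancing by institution was not modelled.

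These cases keep the protocol's medians. Survival in each arm is Σ pₖ exp(−b mₖ t), which depends only on b × t, so multiplying b by 0.75 moves the overall median from 12 to 12/0.75 = 16 months. What changes is that the overall hazard ratio is no longer 1.33 throughout.

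**Step 3. Hold the overall hazard ratio at exactly 1.33, as Protocol 11.2 assumes.** Here overall survival in each arm is exponential with medians of 12 and 16 months, and the strata are linked to survival with latent correlation 0, 0.3 or 0.5. Power is 83.9, 83.5 and 85.0% unstratified, against 83.5, 83.9 and 87.2% stratified. The unstratified test does not fall below 83%.

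**Step 4. How strong can the CD4 stratum be?** For patients assigned by lymphocyte count, Protocol 11.1 gives sensitivity 69%, specificity 81% and prevalence 62%.

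- Truly below 50 among those assigned below 50: 0.62 × 0.69 / (0.62 × 0.69 + 0.38 × 0.19) = 0.4278/0.5000 = 0.856.
- Truly below 50 among those assigned 50 or more: 0.62 × 0.31 / (0.62 × 0.31 + 0.38 × 0.81) = 0.1922/0.5000 = 0.384.
- If lymphocyte count predicts death only through CD4, a true hazard ratio of 2 becomes (0.856 × 2 + 0.144)/(0.384 × 2 + 0.616) = 1.34 between assigned strata at baseline. A true ratio of 3 becomes 1.53. The upper limit is 0.856/0.384 = 2.2.

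The lower and middle rows of CD4 hazard ratio are therefore the more plausible ones for these patients. Patients assigned from CD4 history are not bound by this limit, and the protocol does not give their share.

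**The case against.** The word unstratified does not appear in Protocol 11.3, and a statistical analysis plan that is not shown could add the strata. That stands as far as it goes. But the protocol names its primary test and places covariates in other analyses, so an analysis plan would have to extend the wording.

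A plain log-rank test is a valid prespecified choice, and adjusted Cox models are already planned. Both are true, and they make this a question of efficiency.

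Three stronger readings are tempting and are not supported:

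- A reader might infer that the 83% is wrong. It is not. It reproduces, its condition is stated, and under that condition the unstratified test keeps 83.5–85.0%. A shortfall appears only if 1.33 is taken as the hazard ratio within strata.
- A reader might infer that the interim p-values are invalid. With prognostic strata they are conservative; type I error is not inflated.
- A reader might assume stratum hazard ratios of 2.5 or 3 and infer a much larger loss. The documents give no hazard ratio for death by stratum. For patients assigned by lymphocyte count, a CD4 ratio that large exceeds the 2.2 limit in step 4. The ratios of 2 to 3 in Protocol 11.2 compare disease progression with death, not one CD4 stratum with another.

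How prognostic the strata are remains open. Protocol 7.5 lists CMV disease among conditions chosen for short median survival or high acute mortality, which suggests that stratum matters. Protocol 11.1, however, justifies stratifying on CMV disease by the CMV endpoint, not by survival.

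**Conclusion.** The point holds as an inexpensive improvement, not as a defect that must be corrected. The randomization uses two factors that the primary survival test, on its natural reading, ignores.

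Under the step 2 assumptions, stratifying recovers about 0.4 points of power at stratum hazard ratios of 1.25/1.25 (within simulation error), 1.7 points at 1.5/1.5 and 2.8 points at 2/1.5. With no prognostic effect the two tests are equal within simulation error (84.0 v 83.6%). Under the protocol's own overall hazard ratio of 1.33 the stratified test is about equal or better (83.5–87.2% v 83.5–85.0%). Neither the stated 83% nor the 5% error control is in question.

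**What to change.** In Protocol 11.3, state that the primary log-rank test of overall survival, at each interim look and at the final analysis, is stratified by the two randomization factors: CD4/total lymphocyte count and CMV end organ disease, as recorded at randomization. Do not stratify by institution. Report the hazard ratio from a Cox model stratified the same way, and keep the unstratified log-rank test as a sensitivity analysis. Settle this before the first look at 22 months, so that only one primary p-value is compared with each boundary.

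The cost is a sentence or two of wording and no new data. The small downside is that the estimate becomes a within-stratum hazard ratio, and a small stratum adds little information: under the assumed shares (taken as independent), CD4 of 50 or more with CMV disease holds 640 × 0.38 × 0.20, or about 49 patients. The sample size and the power statement need no change, although 11.2 could say that the 1.33 refers to the overall hazard ratio.
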